3.2. Study Endpoints

3.2.1. Primary Endpoint

• Assessment of DaTSCAN[™] SPECT images by 3 independent blinded readers to compare specific striatal uptake with the clinical diagnosis.

3.2.2. Secondary Endpoints

- Central read (by semi-quantitative assessment by use of DaTQUANTTM) of DaTSCANTM SPECT images to compare specific uptake with clinical diagnosis.
- Comparison and assessment of safety parameters and AEs reported by all study participants.

3.3. Treatments

In this open-label study, each subject will receive 1 dose of the investigational medicinal product (IMP), DaTSCANTM ioflupane (¹²³I) injection, during the imaging visit. Each subject will undergo appropriate thyroid blocking treatment prior to and/or after injection and receive a dose of 111 to 185 MBq DaTSCANTM in a maximum volume of 5 mL. To minimise pain upon injection, the dose will be delivered by a slow IV injection (not less than 15 to 20 seconds) into an arm vein. SPECT imaging should take place between 3 and 6 hours after injection. Details of IMP and procedures are outlined in the protocol Sections 8 and 9.

3.4. Dose Adjustment/Modification

All subjects will be administered the IMP by study personnel. No dose adjustment/ modification is allowed under normal circumstances. Doses administered outside of specific dose requirements or defined range must be reported as protocol deviations.

4. GENERAL STATISTICAL CONSIDERATIONS

4.1. **Reporting Conventions**

Continuous data (absolute values and change from baseline values) will be described using descriptive statistics (i.e. n, mean, standard deviation (SD), median, minimum, and maximum). Categorical data will be described using frequency count and percentage in each category. For the summary statistics of all numerical variables, unless otherwise specified, minimum and maximum will be displayed to the same level of precision as reported. Mean and median will be displayed to one level of precision greater than the data collected. SD/ standard error will be displayed to two levels of precision greater than the data collected. For the summary statistics of categorical variables, all percentages will be rounded to one decimal place. Number and percentage values will be presented as xx (xx.x). If the percentage is 100, no decimal is required. P-values will be rounded to three decimal places. If a p-value is less than 0.001 it will be reported as "<0.001." If a p-value is greater than 0.999 it will be reported as ">0.999." All general and safety analysis and summary tables will have the population sample size in the column headers in the form of N=XXX for the single diagnostic category according to subjects' clinical diagnosis (PS (including PD, MSA, PSP), ET, HV, and all subjects) performed at baseline visit, and the efficacy analysis group for sensitivity, specificity and accuracy are specified in section 8. All enrolled subject data recorded on the case report form (CRF) and entered into the database will be provided in separate data listings showing individual subject values. Data will be displayed in all listings sorted by baseline clinical diagnosis, subject number and visit (time point, if applicable).

All laboratory data will be reported using international system of units (SI).

When count data are presented, the percentage will be suppressed when the count is zero in order to draw attention to the non-zero counts. A row denoted "Missing" will be included in count tabulations where specified on the shells to account for dropouts and missing values. The denominator for all percentages will be the number of subjects in that clinical diagnosis category within the analysis set of interest, unless otherwise specified.

4.2. Baseline and Standard of Truth Definition

The last observation prior to administration of IMP will be used as the baseline value for calculating changes from baseline after administration of IMP.

The clinical diagnosis as established by the investigator at baseline at the recruiting centres according to internationally accepted diagnostic criteria and based on a standardized and comprehensive clinical and neuropsychiatric assessment will be the standard of truth used for determining sensitivity and specificity.

The study day/time will be calculated as assessment date/time – date/time of injection + 1 if the presented date is on or after the date/time of injection. Otherwise, the study day/time will be calculated as assessment date/time – date/time of injection.

4.3. Sample Size Determination

The null hypothesis tests are given as H_0 : $p \le p_0$ where p_0 is the specified threshold. The alternate hypothesis is given by H_a : $p > p_0$. The parameter p represents the sensitivity/specificity of the blinded independent read of DaTSCANTM SPECT images in detecting or excluding SDD, using the clinical diagnosis as established by the investigator as the standard of truth.

An exact binomial test with a nominal 0.05 1-sided significance level will have 80% power to detect the difference between the null hypothesis diagnostic sensitivity threshold of 0.85 and the assumed alternative proportion of 0.95 when the sample size is 59 subjects with SDD present.

An exact binomial test with a nominal 0.05 1-sided significance level will have 80% power to detect the difference between the null hypothesis diagnostic specificity threshold of 0.85 and the assumed alternative proportion of 0.95 when the sample size is 59 subjects with SDD absent.

An extensive set of values for the specified threshold, p_0 , and the resultant sample size (for either sensitivity or specificity) are as follows: $P_0 = 0.89$: n=128; $P_0 = 0.88$: n=107; $P_0 = 0.87$: n= 89;

 $\begin{array}{l} P_0=0.86; \ n=73; \ P_0=0.85; \ n=59; \ P_0=0.84; \ n=55; \ P_0=0.83; \ n=44; \ P_0=0.82; \ n=41; \\ P_0=0.81; \ n=39; \ P_0=0.80; \ n=30. \end{array}$

However, according to regulatory guidelines sample size for a new product with more than 1 indication (which is the case for DaTSCANTM) requires a minimum of 60 pairs of cases. Therefore, the final number of evaluable diseased individuals will be 60 in each group (SDD present and absent).

In addition to the 120 evaluable subjects (subjects with movement disorder), each centre will be requested to recruit 2 to 4 HVs (subjects without movement disorder) for the sole purpose of the creation of a normal database. A total of 20 HVs will be recruited across the centres. These subjects will also be included in the safety analysis.

On the basis of a previous study (DP008-003), it is projected that evaluable results will be obtained for 80% of diseased individuals and 90% of HVs. After adjustment for losses, it is therefore expected that 150 subjects with movement disorders (with or without SDD) and 22 HVs will be needed to provide at least the minimum required number of evaluable subjects.

4.4. Imputation of Incomplete Data

Generally, missing values will not be substituted by estimated values but treated as missing in the statistical evaluation. Available data analysis will be applied to this study. All observed data from all subjects dosed in the study will be included in all listings, plots, summary tables, and statistical analyses when appropriate. Missing and incomplete data for AEs, medical/surgical history, prior and concomitant medication will be specifically imputed according to the following rules for analysis.

Adverse Event

- If onset date is completely missing, then onset date is set to date of IMP injection.
- If onset date's (year is present and month and day are missing) or (year and day are present and month is missing):
 - If year = year of IMP injection, then set onset month and day to month and day of IMP injection
 - \circ If year < year of IMP injection, then set onset month and day to December 31st.
 - \circ If year > year of IMP injection, then set onset month and day to January 1st.
- If onset date's month and year are present and day is missing:
 - o If year=year of IMP injection and
 - If month = month of IMP injection then set day to day of IMP injection date
 - If month < month of IMP injection then set day to last day of month
 - If month > month of IMP injection then set day to 1st day of month
 - If year < year of IMP injection then set day to last day of month
 - If year > year of IMP injection then set day to 1^{st} day of month
- For all other cases, set onset date to date of IMP injection
- If relationship to IMP is missing, AE will be reported separately and the relationship will be evaluated based on AE onset date compared with date of study procedures.
- If Intensity is missing, it will be imputed as Severe.

Medical and Surgical History

- If start date is completely missing then start date will not be imputed.
- If (start year is present and start month and start day are missing) or (start year and start day are present and start month is missing) then set start month and start day to January 1.
- If start year and start month are present and start day is missing then set start day to 1st day of month.
- If end date is completely missing then end date will not be imputed.

Confidential and Proprietary

GE-001-024 Statistical A Version 1.0 Approved

Statistical Analysis Plan. Protocol GE-001-024

• If (end year is present and end month and end day are missing) or (end year and end day are present and end month is missing) then set end month and end day to December 31.

n

• If end year and end month are present and end day is missing then set end day to last day of the month.

Prior and Concomitant Medications

- If start date is completely missing then start date will not be imputed.
- If (start year is present and start month and start day are missing) or (start year and start day are present and start month is missing) then set start month and start day to January 1.
- If start year and start month are present and start day is missing then set start day to 1st day of month.
- If end date is completely missing then end date will not be imputed.
- If (end year is present and end month and end day are missing) or (end year and end day are present and end month is missing) then set end month and end day to December 31.
- If end year and end month are present and end day is missing then set end day to last day of the month.

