10.3.5 Adverse events

All AEs/SAEs that occur after informed consent shall be recorded in the AE/SAE report form (see the Study Schedule of Events, Table 1).

Study personnel must remain vigilant for the occurrence of AEs after administration of IMP, particularly those that may be life threatening. Personnel who are trained in the acute management of anaphylaxis and other emergencies and who have access to appropriate clinical supplies must be immediately available for 1 hour after dosing. Treatment of SAEs should be primarily supportive of vital functions.

AE and DaTSCANTM-emergent AE definition: An AE is defined as any untoward medical occurrence or an already present event that worsens either in intensity or frequency. A DaTSCANTM-emergent AE is defined as an AE that starts on or after the time of the injection of DaTSCANTM until the follow-up visit at 3 (±1) days later. The DaTSCANTM-emergent AE does not necessarily have to have a causal relationship with exposure to the investigational agent. A DaTSCANTM-emergent AE can therefore be any unfavourable and unintended sign (including an abnormal laboratory finding), symptom, or disease temporally associated with the exposure to the IMP, whether or not considered related to that product.

The subjects will be closely observed and questioned for any kind of AE during the study procedures and throughout the study period with non-leading questioning (e.g., "How do you feel?"). The subjects will be instructed to immediately report any symptoms and signs to the study staff (i.e., between formal observations).

If an AE has already been reported it is not necessary to report each individual sign and symptom of that AE as a separate AE. For example, if myocardial infarction is reported as an AE, there is no need to report an elevated creatine phosphokinase, abnormal ECG, or other related signs, symptoms, or laboratory values as separate AEs.

All AEs/SAEs and all DaTSCANTM-emergent AEs/SAEs shall be collected up to the time point of finalisation of the last safety examination during the follow-up performed at 3 (± 1) days post-injection.

Causal relationship

Both the investigator(s) and Sponsor/contract research organisation (CRO) will perform a causality assessment on any AE, to assess whether or not there is a reasonable possibility (evidence to suggest) that the IMP caused the event.

The relationship of an AE with DaTSCANTM will be assessed and reported by the investigator as:

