9.1. Adverse Events

An AE is defined as any untoward medical occurrence or an already present event that worsens either in intensity or frequency. A DaTSCANTM-emergent AE, globally defined as treatmentemergent AE (TEAE), is defined as an AE that starts on or after the time of the injection of DaTSCANTM until the follow-up visit at 3 (\pm 1) days later regardless of its causal relationship to investigational agent, therefore it can be any unfavourable and unintended sign (including an abnormal laboratory finding), symptom, or disease temporally associated with the exposure to the IMP, whether or not considered related to that product. A serious adverse event (SAE) is defined as any event that results in death, is immediately life threatening, requires inpatient hospitalization or prolongation of existing hospitalization, results in persistent or significant disability/incapacity, is a congenital anomaly/birth defect, or is another important medical event defined in protocol Section 10.3.5.1. Other significant AEs are defined as laboratory abnormalities that qualify as AEs (other than those meeting the definition for serious) and any events that lead to an intervention (including premature discontinuation of IMP, dose reduction, or significant additional concomitant therapy).

AE terms recorded by the clinical site will be mapped to SOC and PT using MedDRA version 22.0 or later. If the start date, end date, severity, or relationship of AE is missing, it will be imputed as shown in Section 4.4.

The following summaries of AEs by SOC and PT will be provided:

- All AEs
- All TEAEs
- All SAEs
- All treatment-emergent SAEs
- All TEAEs resulting in study treatment discontinuation
- All related TEAEs
- All related treatment-emergent SAEs
- All other significant AEs
- All TEAEs by intensity
- All treatment-emergent SAEs by intensity
- All most common AEs (defined as AEs reported by at least 5% of the subjects).

If a subject experiences the same AE more than once with different intensity (mild, moderate, and severe), then the event with the highest intensity will be tabulated in "by intensity" tables. If a subject experiences multiple TEAEs under the same PT (or SOC), then the subject will be counted only once for that PT (or SOC).

In summary tables, AEs are sorted by alphabetical order of SOC, and then descending frequencies of PT.

Data listings will be provided for all AEs. The incidence of deaths and the primary cause of death will be displayed in a listing.

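### SAP 4.4 can set an AE onset to the injection date although the AE is recorded as having ended before injection, so the event counts as DaTSCAN-emergent with an onset after its end

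*SAP*

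**What the plan says.** SAP 4.4 gives the AE onset rules. The injection date is used in four situations:

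- Onset wholly missing: "If onset date is completely missing, then onset date is set to date of IMP injection".
- Month missing, with or without a day: "If year = year of IMP injection, then set onset month and day to month and day of IMP injection".
- Only the day missing, in the injection year: "If month = month of IMP injection then set day to day of IMP injection date".
- Everything else: "For all other cases, set onset date to date of IMP injection".

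Other partial dates are handled differently. For an earlier month of the injection year, "If month < month of IMP injection then set day to last day of month". For an earlier year, onset goes to the last day of the known month, or to 31 December if the month is unknown.

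None of these rules refers to the AE end date. SAP 9.1 then defines a DaTSCAN-emergent AE by onset: it "is defined as an AE that starts on or after the time of the injection of" DaTSCAN, up to the follow-up visit. There is no exception for an event that ended before injection.

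AEs are collected before dosing. Protocol 10.3.5 says "All AEs/SAEs that occur after informed consent shall be recorded in the AE/SAE report form", and Protocol 9.1 allows screening up to 28 days before imaging.

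SAP 9.1 also says "If the start date, end date, severity, or relationship of AE is missing, it will be imputed as shown in Section 4.4". Section 4.4 has end-date rules for medical and surgical history and for medications, but none for AEs.

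**The concern.** Counting an event as emergent when its timing is unclear is a sound conservative convention. An event with a recorded end before injection is not unclear: the database already shows that it did not start after dosing. Applied as written, the rule overrides that information and gives a record whose onset is later than its end.

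The emergent AE tables and the AE listings would be affected. A missing relationship could be affected too, because SAP 4.4 has it judged by comparing the onset date with the dates of study procedures, and a false injection-day onset could influence that judgement. A programmer who notices the impossible dates must either keep them or make up an exception that the SAP does not specify.

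**Working it through.** The documents give no figure on this point, so there is nothing to reproduce. The check applies the SAP 4.4 rules literally.

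**Inputs.** Onset rules from SAP 4.4; emergent definition from SAP 9.1; up to 28 days from screening to imaging from Protocol 9.1; planned enrolment of 150 patients and 22 healthy volunteers (HVs), 172 in all, from SAP 4.3.

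**Single cases, each with a known end date**

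| Recorded onset | Recorded end | Injection | Imputed onset | Emergent? | Onset after end? |
|---|---|---|---|---|---|
| March | 10 March | 20 March | 20 March | yes | yes, by 10 days |
| missing, year only, or June | 10 June | 20 June | 20 June | yes | yes, by 10 days |
| May | 10 May | 20 June | 31 May | no | yes, by 21 days |
| May | 10 June | 20 June | 31 May | no | no |

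**All cases in one calendar year.** The rules were applied to every injection date in 2021, with true onset 1 to 28 days before injection and a known end anywhere from onset to the day before injection. That is 365 × (1 + 2 + … + 28) = 365 × 406 = 148,190 combinations, equally weighted.

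| Part of onset missing | Counted as emergent | Onset after end |
|---|---|---|
| whole date | 100% | 100% |
| month, or month and day | 94.8% | 97.3% |
| day only | 37.5% | 67.1% |

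None of these events is truly emergent. The calendar year and equal weighting are assumptions, so the percentages show how each rule behaves and are not expected rates. In the day-only row, the emergent share is below the onset-after-end share because the rules for an earlier month or year keep an event pre-injection but can still place its onset after its end.

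**With a cap.** Taking the imputed onset as the earlier of the rule's date and the known end date brings both columns to 0% in every row.

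**Effect of one case on incidence.** Overall: 1/172 = 0.58%, about 0.6 points. HVs: 1/22 = 4.5 points. This assumes that all planned subjects are dosed and that the subject has no other emergent AE.

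**The case against.** The strongest reply is that this hardly matters. It takes an event with a known end but an incomplete onset, arising within about four weeks of imaging, at sites that ask about AEs at every visit and whose data undergo quality control. Safety is descriptive, with no testing (Protocol 12.6.1, SAP 9). All AEs are also tabulated and listed whatever their timing. The error can only raise the emergent count, in keeping with SAP 4.4 imputing a missing intensity as severe. All of this stands, and it limits the importance of the point. It does not justify a rule that contradicts recorded data when the correction leaves the conservative default in place.

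The gap on AE end dates is smaller still. The general default in SAP 4.4 is to leave missing values missing, and no AE summary listed in SAP 9.1 uses the end date. It is a cross-reference with no target.

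A reader might infer more than the documents support:

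- *That every partial onset date goes to the injection date.* It does not; dates with a known earlier month or year stay before injection.
- *That 28 days of collection before injection against 2 to 4 days after makes a month-only date 7 to 14 times as likely to be pre-injection.* The ratios 28/4 and 28/2 compare full windows, whereas a month-only date sent to the injection date must lie in the injection month. With a 30-day month and a uniformly distributed injection day (assumptions), the in-month averages are about 14.5 days before and 3.7 or 1.9 days after, a ratio of about 4 to 8. Even that uses the 28-day maximum and treats days as if they were AE rates. Such events without a recorded earlier end are also the ambiguous ones, for which the existing rule is defensible.

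**Conclusion.** The point holds, as a minor one. For an AE recorded as ended before injection, SAP 4.4 and SAP 9.1 together give a wrong classification whenever the onset date is wholly missing, matches the injection date in its known parts as described above, or falls under the residual rule. For earlier known months or years the classification is right, but the imputed onset can still fall after the recorded end.

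The direction is certain: emergent AEs can only be over-counted. The size is not known, because the documents do not say how many onset dates will be incomplete; it is probably small. The per-case increments of about 0.6 points overall and 4.5 points in HVs do not apply to a subject who already has a genuine emergent AE, since that subject is already in the overall incidence. Efficacy is untouched. A reader might infer that the rule hides a safety signal or undermines the safety conclusions; an error that only adds emergent events to descriptive tables does not support that.

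**What to change.** Add to SAP 4.4, after the AE onset rules:

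> If the latest date consistent with the recorded AE end date is before the injection date, the AE is not treatment-emergent, and the imputed onset is the earlier of the date given by the rules above and that end date; otherwise the existing rules apply.

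This assigns a value that can be programmed, copes with partial end dates, and leaves the conservative default for events whose end is unknown, ambiguous, or on or after the injection date.

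As a tidy-up, either remove the end date from the SAP 9.1 cross-reference or add an AE end-date rule to Section 4.4.

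The cost is a sentence or two in the SAP and one programming check. No new data are needed, and sample size, error rates and clinical procedures do not change.

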4.5. Randomization

No randomization will take place in this open-label study.

4.6. Analysis Sets

The Enrolled population for this study includes all subjects enrolled, i.e., who meet the inclusion/exclusion criteria and are dosed with DaTSCANTM ioflupane (¹²³I).

The following analysis sets will be used in the statistical analyses.

Full-analysis set (FAS): The efficacy analysis will be performed for the FAS, which will consist of all subjects who have both a DaTSCANTM image set and a clinical diagnosis made by the investigator.

Per-protocol (PP) population: The PP population will include subjects in the FAS who comply with the following conditions:

- Meet the inclusion/exclusion criteria, and did not withdraw informed consent (if applicable)
- Have DaTSCANTM image sets that are considered evaluable by at least 2 of the 3 blinded readers
- No major protocol violations

Safety population: All subjects who receive an injection of IMP will be included in the safety population.

For this study, efficacy analyses will be performed on both the FAS and PP populations, and safety analyses will be performed on the safety population.

